2.0 Study Objectives

Primary Aim: To determine if gabapentin provides symptom relief for chronic irritability in neurologically impaired children despite medical management for identified sources of symptoms or if no etiology is identified,

Primary Hypothesis: Gabapentin is beneficial and safe for neurologically impaired children with chronic irritability that persists despite identification and appropriate management of symptom sources.

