8.5 Stopping Rules.....	36
8.6 Medical Monitoring	36
9.0 Data Handling and Record Keeping	36
9.1 Confidentiality	36
9.2 Source Documents	37
9.3 Case Report Forms.....	37
9.4 Records Retention.....	37
10.0 Study Monitoring, Auditing, and Inspecting	37
10.1 Study Monitoring Plan.....	37
10.2 Auditing and Inspecting.....	38
11.0 Ethical Considerations	38
12 Study Finances	39
12.1 Funding Source	39
12.2 Conflict of Interest	39
12.3 Subject Stipends or Payments	39
13 Publication Plan	39
14 References.....	39
15 Attachments	40

List of Abbreviations

AE	Adverse Event
CFR	Code of Federal Regulations
CRF	Case Report Form
FDA	Food and Drug Administration
GCP	Good Clinical Practice
HIPAA	Health Insurance Portability and Accountability Act of 1996
ICH	International Conference on Harmonization
IDS	Investigational Drug Service
IRB	Institutional Review Board
ITT	Intent to Treat
NCCPC-R	Non-Communicating Children's Pain Checklist-Revised
PHI	Protected Health Information
REPA	Report of External Professional Activities
SAE	Serious Adverse Event
UPIRTSO	Unanticipated Problems Involving Risk to Subjects or Others

Study Summary

Title	A phase II, randomized, placebo-controlled, double blind, cross-over, study of the effects of Gabapentin on chronic irritability in neurologically impaired children
Short Title	Effects of Gabapentin on chronic irritability in neurologically impaired children.
Phase	Phase II
Methodology	The study is a randomized, placebo-controlled cross-over.
Study Duration	The estimated duration of the study is 12 months
Study Center(s)	This is a single center study to be conducted at Gillette Children's Specialty Hospital, [name].
Objectives	To determine if gabapentin provides symptom relief for chronic irritability in neurologically impaired children despite medical management for identified sources of symptoms or if no etiology is identified.
Number of Subjects	40 evaluable subjects
Diagnosis and Main Inclusion Criteria	Neurological impairment and chronic irritability suggesting pain.
Study Product, Dose, Route, Regimen	Gabapentin (Neurontin®), to be administered as an oral solution titrated over a 22 day period, followed by a 7 day stable dose period (40 mg/kg/day over 3 dosages), followed by a 9 day taper and washout period
Duration of administration	Subjects will receive drug for 34 days, and placebo for 34 days, with a 3 day washout period in between.

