5.5 Subject Compliance Monitoring

Compliance will be monitored by having the parents of the subject bring any unused drug back to Gillette Children's Specialty Healthcare each time they visit for the study. Amount of unused drug will be measured by the pharmacy before the subjects can get their next supply of study drug. Subjects will also be called every two weeks to assess any AEs and any positive effects subjects are experiencing. They will be asked how the customized drug plan for them is working. If a subject is found to be noncompliant with the study drug, the subject will be withdrawn from the study, with all withdrawal procedures followed. A subject will be defined as noncompliant if more than three days of doses of drug are missed.

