7.0 Statistical Plan

7.1 Sample Size Determination

Power Calculations: A minimum sample size of 40 patients was determined by estimating a 15 point difference using the NCCPR-R pain assessment tool (90 points total) pre and post gabapentin, with a SD of 25 and within-person correlation of 0.6, accounting for recruitment and retention.

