7.2 Statistical Methods

Simple descriptive statistics will be utilized to compare differences between the treatment and placebo groups with respect to frequency and duration of pain episodes, and frequency of gastrointestinal and sleep problems. Parent/caregiver reported questionnaires will be compared between groups. The NCCPR-R assessments will be scored and compared between groups, with a 15 point difference considered a significant difference.

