7.3 Subject Population(s) for Analysis

The subject population to be analyzed includes all protocol compliant subjects. Subjects who are not compliant with the protocol will be withdrawn as described in Section 5.5

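### The primary hypothesis calls gabapentin safe, but Section 7 plans no adverse event comparison and its only analysis population is the protocol-compliant children

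*SAP*

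**What the plan says.** SAP Section 2.0 gives an aim and a hypothesis that differ in scope. The primary aim is "To determine if gabapentin provides symptom relief for chronic irritability in neurologically impaired children". The primary hypothesis is that "Gabapentin is beneficial and safe for neurologically impaired children with chronic irritability". The plan attaches no definition, endpoint or threshold to the word safe.

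The rest of the plan follows the aim:

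- Sections 3.2 and 3.3 list diagnostic yield, pain, gut and sleep problems, the pain checklist, parental satisfaction and timing relative to surgery. Neither lists adverse events.
- Section 7.1 sizes the trial on the pain checklist alone: "A minimum sample size of 40 patients was determined by estimating a 15 point difference".
- Section 7.2 begins "Simple descriptive statistics will be utilized to compare differences between the treatment and placebo groups" and goes on to pain episodes, gut and sleep problems, caregiver questionnaires and the checklist score.
- Section 7.3 states "The subject population to be analyzed includes all protocol compliant subjects" and names no other population.
- Section 5.5 sets the compliance limit, "A subject will be defined as noncompliant if more than three days of doses of drug are missed", and has such a child withdrawn.

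Section 8 separately requires all adverse events to be recorded, sets a reporting period that runs to 30 days after the last administration, and provides for medical monitoring and stopping rules.

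**The concern.** The primary hypothesis makes two claims, and the analysis plan addresses one of them. For the other, the only population rule in Section 7 depends on something that happens after randomisation and that side effects can plausibly cause. Section 1.5 lists somnolence, vomiting, hostility and emotional lability among the known risks. These are credible reasons for a caregiver to stop giving doses, and several resemble the symptoms under study. Without a placebo-period contrast they are hard to tell from the child's background condition.

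At stake is how a favourable safety statement would be read. If it came from the Section 7 population, it would describe children who kept taking the drug and would have no planned comparator.

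**Working it through.** **1. What the sample size was built for.** The inputs in Section 7.1 are a 15-point difference, "with a SD of 25 and within-person correlation of 0.6, accounting for recruitment and retention". For a paired comparison:

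- SD of the within-child difference = 25 × √(2 × (1 − 0.6)) = 22.36.
- n = (22.36 × (z_α + z_power) / 15)². Two-sided 5% with 80% power gives 18 (20 with the t correction). With 90% power it gives 24 (26).

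The plan states no alpha, power or attrition rate, so 40 can be neither confirmed nor refuted. It is reached, for example, as 20 / (1 − 0.5) or 24 / (1 − 0.4). Forty completers would have about 98.5% (t) to 98.9% (normal) power. The number is ample for the checklist on these inputs, and nothing in it relates to safety.

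**2. How the population rule acts.** Section 5.5 withdraws a child above the missed-dose limit whatever the reason, and Section 7.3 then excludes that child. Section 4.5.2 names only survival contact for withdrawn children, while Section 8 has no compliance filter. The events are therefore recorded, but the child is outside the Section 7 comparisons.

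The possible distortion can be bounded but not estimated. Assume 40 children exposed to gabapentin and no event of some type among the compliant ones:

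| Compliant (assumed) | Excluded | Rate in compliant | Possible rate in all exposed |
|---|---|---|---|
| 36 | 4 | 0/36 = 0% | 0% to 4/40 = 10% |
| 30 | 10 | 0/30 = 0% | 0% to 10/40 = 25% |

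The upper ends are extremes in which every excluded child had the event.

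**3. What a clean result would exclude.** With zero events in n children, the exact upper limit is 1 − 0.05^(1/n) (one-sided 95%) or 1 − 0.025^(1/n) (two-sided 95%).

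| n | One-sided | Two-sided |
|---|---|---|
| 40 | 7.2% | 8.8% |
| 36 | 8.0% | 9.7% |
| 30 | 9.5% | 11.6% |

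These limits apply only to zero events. With one event in 40, the one-sided limit solves (1 − p)^40 + 40p(1 − p)^39 = 0.05, which gives about 11.3%.

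The chance of seeing at least one event in 40 is 1 − (1 − p)^40, which is 33%, 55% and 87% for true risks of 1%, 2% and 5%. Excluding risks of 5%, 2% or 1% with zero events (one-sided 95%) takes ln(0.05)/ln(1 − p), or 59, 149 and 299 children.

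**4. What a paired comparison could show.** The table gives the power of an exact two-sided McNemar test with 40 children exposed in both periods, assuming independent risks within child. The rates are assumptions, because the documents give none for these children.

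| Placebo | Gabapentin | Power |
|---|---|---|
| 5% | 10% | 4% |
| 5% | 20% | 39% |
| 5% | 30% | 80% |
| 10% | 20% | 15% |
| 10% | 40% | 84% |

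Forty children could reveal a very large difference in a common side effect, but not a moderate one.

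**The case against.** The strongest reply is that safety is handled in Section 8. All adverse events are recorded regardless of compliance, unresolved events are followed, serious events are reviewed regularly, and a serious event attributable to gabapentin interrupts or stops the study. That stands. A reader might infer that a noncompliant child's side effects vanish from the trial. The documents do not support this, because the loss is confined to the Section 7 comparisons. However, Section 8 covers recording, reporting and oversight. It plans no contrast with placebo and sets no criterion for safe.

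Second, Section 7.2 does compare gut and sleep problems between treatments, and these overlap in part with the listed risks. Section 6.0 also has side effects discussed with the family after each period. So it would be too much to say that no tolerability contrast exists. What is missing is a comparison of adverse events as such.

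Third, the primary aim is already limited to symptom relief, and a phase II trial need not prove safety. Both points are fair, and they argue for bringing the hypothesis into line with the aim.

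Fourth, the zero-event limit would hold for any 40 patients and is a poor yardstick for common tolerability effects. That also stands. The limit is useful only for saying what uncommon harms remain open.

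**Conclusion.** The point holds as a mismatch within the plan. Safety is part of the primary hypothesis, no adverse event comparison is planned, and the sole analysis population would tilt any safety conclusion towards children who tolerated the drug. It should be corrected, but the efficacy analysis does not depend on it.

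The size of the tilt is unknown. It rests on the assumption that some children miss more than three days of doses because of side effects, which is plausible but not quantified in the documents.

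Two stronger readings are tempting. One is that nothing in the design could support a statement of safety, or that 40 children are too few for one. The plan sets no threshold for safe, so this cannot be shown. What can be shown is that uncommon harms, and moderate differences in common ones, would remain unresolved. The other is that rates below about 7% can never be excluded. That figure is one-sided and holds only if no event is seen in 40 exposed children. The number exposed may also differ from the "40 evaluable subjects" in the Study Summary: dosed children can outnumber evaluable ones, and a child who leaves during a first placebo period never takes gabapentin.

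**What to change.** - **Section 2.0:** limit the primary hypothesis to benefit, and state tolerability as a descriptive objective.
- **Section 7.3:** add a safety population of every child given at least one dose, including withdrawn and noncompliant children.
- **Section 7.2:** report adverse events, serious adverse events and discontinuations per child, by the treatment being taken when they occurred. Use the number exposed to each treatment as the denominator, with exact 95% confidence intervals. State in advance how an event that starts in the off-drug days between periods is assigned.
- **Paired difference:** give the gabapentin-placebo difference only as a supplement, for children exposed in both periods. It leaves out those who stop in the first period, so it cannot be the main safety summary.
- **Interpretation:** add a conditional sentence. If no event of a given type is seen in 40 exposed children, the exact 95% upper limit is about 7.2% (one-sided) or 8.8% (two-sided), so uncommon harms cannot be excluded. Recompute it for the number actually exposed.

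The cost is one extra table, some wording and a weaker safety claim. No new data collection is needed, because Section 8 already requires the events to be recorded.

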3.0 Study Design

3.1 General Study Design

The design of this study is a prospective, randomized, double blind, placebo-controlled, crossover clinical trial. The study will involve a 22-day medication/placebo titration period, 7-day stable dosing, 9-day taper and washout, followed by crossover. The length of the study is 12 months.

3.2 Primary Study Endpoints

Evaluation and Outcome Measures:

- Frequency and results of diagnostic studies obtained for evaluation of cause of pain/irritability with analysis of yield of testing
- Parental reporting of frequency and duration of pain episodes
- Parental reporting of associated gastrointestinal and sleep problems
- Symptom assessment using the NCCPC-R (Non-Communicating Children's Pain Checklist-Revised), a standardized pain assessment tool for nonverbal neurologically impaired children, validated to be significantly related to pain intensity ratings provided by caregivers, consistent over time, and sensitive and specific to pain
- Parental satisfaction

3.3 Secondary Study Endpoints

Secondary Aims:

- To describe results of diagnostic studies obtained in neurologically impaired children with chronic irritability
- To identify associated gastrointestinal and sleep problems
- To determine if start or escalation of symptoms is temporally related to surgical interventions

Secondary Hypotheses:

- Repeating diagnostic studies when irritability persists adds limited benefit
- Gastrointestinal symptoms (feeding intolerance and symptoms associated with gas and bowel movements) and disrupted sleep are frequently associated with chronic irritability and improve with gabapentin

Escalation of symptoms often has a temporal relationship with a surgical procedure.

4.0 Subject Selection and Withdrawal

4.1 Inclusion Criteria

Subjects are eligible to participate in the study if all of the following conditions exist:

1. Male or female, age 1 month to 16 years at enrollment
2. Neurological impairment defined as subnormal (-2 S.D.) motor and/or cognitive ability from a variety of etiologies
3. Chronic irritability defined as symptoms suggesting pain to the child's caregiver occurring recurrently over a 4-week or greater time period
4. Subject must have an acceptable surrogate capable of giving consent on the subject's behalf

4.2 Exclusion Criteria

Subjects will be excluded from participation in the study if any of the following conditions exist:

1. Children with resolved symptoms after treatment of identified sources
2. Identified potential source of irritability without adequate trial of appropriate management
3. Ketogenic diet
4. Renal insufficiency or failure
5. Current treatment with gabapentin or pregabalin for another existing condition

4.3 Exit Criteria

Subjects will exit the study if any of the following conditions exist:

1. Subject voluntarily withdraws from the study.
2. Subject death.
3. Subject acquires any of the listed exclusion criteria.
4. Subject completes the protocol.
5. Subject is non-compliant with the study protocol. Subject non-compliance is defined in Section 5.5.

Subjects exiting the study prior to completion of the protocol will be withdrawn as per Section 4.5.

4.4 Subject Recruitment and Screening

Gillette Children's Specialty Healthcare clinicians and nurses that treat children with neurological impairment will be informed of the study. Targeted clinics within Gillette include pediatric neurology, pediatric gastroenterology, and pediatric pain, along with other pediatric clinics that provide a model of chronic care for children with chronic complex medical conditions. If a patient is seen within a clinic that has been informed of the study, an introduction letter for the study will be handed out to potential candidate families. Database searches will also be conducted for potential

subjects. If a candidate is found in a database search, that family will be mailed the introduction letter, and receive a follow-up telephone call two weeks later to determine if the family is interested. The introduction letter will also contain contact information for the investigators and the clinical research coordinator.

4.5 Early Withdrawal of Subjects

4.5.1 When and How to Withdraw Subjects

Subjects may withdraw from the study at any time by withdrawing their consent. They must agree to be contacted (for safety reasons) for survival data. Subjects who do not adhere to the study drug dosing may also be withdrawn from the study to preserve the data collection.

If the subject withdraws from the study, it will be recommended to titrate off the medication per the chart depending on current dose.

4.5.2 Data Collection and Follow-up for Withdrawn Subjects

Subjects who are withdrawn from the study will be contacted for survival data. At least 5 phone calls will be attempted, after which 3 letters will be sent from the site. Subjects who do not answer these calls or letters will be considered lost to follow-up. We will attempt to determine any deaths via our databases, newspaper announcements, and telephone listings for parents.

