8.0 Safety and Adverse Events

8.1 Definitions

Adverse Event

An *adverse event* (AE) is any symptom, sign, illness or experience that develops or worsens in severity during the course of the study. Intercurrent illnesses or injuries should be regarded as adverse events. Abnormal results of diagnostic procedures are considered to be adverse events if the abnormality:

- results in study withdrawal.
- is associated with a serious adverse event.
- is associated with clinical signs or symptoms.
- leads to additional treatment or to further diagnostic tests.
- is considered by the investigator to be of clinical significance.

Serious Adverse Event

A ***serious adverse event (SAE)*** is any AE that is:

- fatal.
- life-threatening.
- requires or prolongs hospital stay.
- results in persistent or significant disability or incapacity.
- a congenital anomaly or birth defect.

Important medical events may be considered SAEs. Important medical events are those that may not be immediately life threatening, but are clearly of major clinical significance. They may jeopardize the subject, and may require intervention to prevent one of the other serious outcomes noted above. For example, drug overdose or abuse, a seizure that did not result in in-patient hospitalization, or intensive treatment of bronchospasm in an emergency department would typically be considered serious.

Adverse Event Reporting Period

The study period during which adverse events must be reported is normally defined as the period from the initiation of any study procedures to the end of the study treatment follow-up. For this study, the study treatment follow-up is defined as 30 days following the last administration of study treatment.

Preexisting Condition

A preexisting condition is one that is present at the start of the study. A preexisting condition should be recorded as an adverse event if the frequency, intensity, or the character of the condition worsens during the study period.

General Physical Examination Findings

At screening, any clinically significant abnormality should be recorded as a preexisting condition. At the end of the study, any new clinically significant findings/abnormalities that meet the definition of an adverse event must also be recorded and documented as an adverse event.

Post-study Adverse Event

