All unresolved adverse events should be followed by the investigator until the events are resolved, the subject is lost to follow-up, or the adverse event is otherwise explained. At the last scheduled visit, the investigator should instruct each subject to report any subsequent event(s) that the subject, or the subject's personal physician, believes might reasonably be related to participation in this study.

Abnormal Laboratory Values

A clinical laboratory abnormality should be documented as an adverse event if any one of the following conditions is met:

- The laboratory abnormality is not otherwise refuted by a repeat test to confirm the abnormality
- The abnormality suggests a disease and/or organ toxicity
- The abnormality is of a degree that requires active management; e.g. change of dose, discontinuation of the drug; more frequent follow-up assessments, further diagnostic investigation, etc.

Hospitalization, Prolonged Hospitalization or Surgery

Any adverse event that results in hospitalization or prolonged hospitalization should be documented and reported as a serious adverse event unless specifically instructed otherwise in this protocol. Any condition responsible for surgery should be documented as an adverse event if the condition meets the criteria for an adverse event.

Neither the condition, hospitalization, prolonged hospitalization, nor surgery are reported as an adverse event in the following circumstances:

- Hospitalization or prolonged hospitalization for diagnostic or elective surgical procedures for a preexisting condition. Surgery should not be reported as an outcome of an adverse event if the purpose of the surgery was elective or diagnostic and the outcome was uneventful.
- Hospitalization or prolonged hospitalization required to allow efficacy measurement for the study.
- Hospitalization or prolonged hospitalization for therapy of the target disease of the study, unless it is a worsening or increase in frequency of hospital admissions as judged by the clinical investigator.

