9.0 Data Handling and Record Keeping

9.1 Confidentiality

Information about study subjects will be kept confidential and managed according to the requirements of the Health Insurance Portability and Accountability Act of 1996 (HIPAA). Those regulations require a signed subject authorization informing the subject of the following:

- What protected health information (PHI) will be collected from subjects in this study
- Who will have access to that information and why
- Who will use or disclose that information
- The rights of a research subject to revoke their authorization for use of their PHI.

In the event that a subject revokes authorization to collect or use PHI, the investigator, by regulation, retains the ability to use all information collected prior to the revocation of subject authorization. For subjects that have revoked authorization to collect or use PHI, attempts should be made to obtain permission to collect at least vital status (i.e. that the subject is alive) at the end of their scheduled study period.

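### For formally withdrawn children the plan names survival as the only follow-up, so symptom scores, the reason for stopping and planned adverse event contact are lost, and 4.5.2 is not aligned with 8.1 and 8.2

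*SAP*

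**What the plan says.** The document calls itself a protocol in 1.0 and has its own section on data collection after withdrawal, so this rule is stated here rather than left to another document.

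- **What is sought after withdrawal.** 4.5.2: "Subjects who are withdrawn from the study will be contacted for survival data". The site makes at least 5 calls, then sends 3 letters, and also searches for deaths: "We will attempt to determine any deaths via our databases, newspaper announcements, and telephone listings for parents". 4.5.1 says of those who withdraw consent: "They must agree to be contacted (for safety reasons) for survival data".
- **Who is withdrawn.** Families may leave at any time. For missed doses, 4.5.1 is permissive: "Subjects who do not adhere to the study drug dosing may also be withdrawn from the study to preserve the data collection". 5.5 is not: "If a subject is found to be noncompliant with the study drug, the subject will be withdrawn from the study". 5.5 sets the threshold at more than three days of missed doses, and 4.3 lists non-compliance as an exit criterion.
- **What the trial measures.** The endpoints in 3.2 and the secondary aims in 3.3 cover NCCPC-R, pain episodes, gastrointestinal and sleep problems, diagnostic yield, parental satisfaction and timing relative to surgery. Survival is in neither list. The primary hypothesis in 2.0 covers both benefit and safety.
- **Adverse events.** Under 8.1, "the study treatment follow-up is defined as 30 days following the last administration of study treatment", and "All unresolved adverse events should be followed by the investigator until the events are resolved, the subject is lost to follow-up". 8.2 requires every event in the study period to be recorded. Neither section mentions withdrawn children.
- **Analysis set.** 7.3 analyses protocol-compliant subjects.

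**The concern.** The follow-up effort goes to an outcome the trial does not study, and none is assigned to the outcomes it does study. A child whom the site withdraws for missed doses has a caregiver who has not withdrawn consent, so nothing in the plan prevents asking that caregiver for the short forms or the reason for stopping.

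The loss is plausibly informative. A caregiver may skip doses because the child is drowsy or because nothing has improved, and either reason bears on the primary hypothesis. 7.3 compounds this by leaving such children out of the analysis. An analysis set can be changed later, but scores that were never collected cannot be recovered.

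There is also a safety side. 4.5.1 recommends a taper after withdrawal, so exposure may continue when survival is the only contact that 4.5 names.

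**Working it through.** **1. The sections side by side**

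| Item | Named after withdrawal in 4.5? | Required or used elsewhere? |
|---|---|---|
| Survival | Yes | Not an endpoint (3.2, 3.3) |
| NCCPC-R, Questionnaire #2 | No | Endpoint data (3.2, 6.0) |
| Main reason for stopping | No | Not asked for; 9.3 only wants missing CRF data explained |
| Adverse events to 30 days | No | Required (8.1, 8.2) |

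**2. What is lost, by time of withdrawal.** The schedule in 6.0 has NCCPC-R at Days 0, 13, 24, 34–37, 51 and 62, six in all. Withdrawal just after Day 13 loses 4 of 6, after Day 24 it loses 3, after Days 34–37 it loses 2, and after Day 51 it loses 1. A child withdrawn after Day 51 already has a Day 13/Day 51 pair.

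**3. Adverse event window.** Period 2 starts on Day 38 and has 34 dosing days, so the last dose falls on Day 37 + 34 = 71. Adding 30 days gives Day 101. The last scheduled contact is Day 76, 25 days short, so the schedule does not reach the end of the 8.1 window even for completers. For a withdrawn child no contact tied to that window is named.

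**4. Power or bias?** Inputs from 7.1: difference 15, SD 25, within-person correlation 0.6. Alpha, power and the retention allowance are not stated, so the figure of 40 can be neither confirmed nor refuted. I assume two-sided alpha 0.05 and a paired comparison.

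- SD of the paired difference = 25 × √(2 × (1 − 0.6)) = 22.36.
- n = (22.36 × (z₀.₉₇₅ + z_power) / 15)². This gives 18 at 80% power, 24 at 90% and 29 at 95%. The exact paired t test needs 20, 26 and 31.

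For bias, let a proportion w be withdrawn, with a difference of 15 in completers and d in withdrawn children. The mean over all children is 15(1 − w) + d·w. Both w and d are assumptions.

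| w | Pairs left of 40 | Paired-t power | Mean if d = 0 | d = 7.5 | d = 15 |
|---|---|---|---|---|---|
| 0% | 40 | 98.5% | 15 | 15 | 15 |
| 10% | 36 | 97.5% | 13.5 | 14.25 | 15 |
| 20% | 32 | 95.7% | 12.0 | 13.5 | 15 |
| 40% | 24 | 88.2% | 9.0 | 12.0 | 15 |
| 50% | 20 | 81.2% | 7.5 | 11.25 | 15 |

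The table counts every withdrawal as a lost pair, which overstates the power loss (step 2). If 40 is the evaluable number, as the Study Summary says, power stays at 98.5%. In either case power holds up well, while the mean can fall below the 15 points that 7.2 takes as significant. If withdrawn children respond as completers do (d = 15), there is no bias. The plan collects nothing after withdrawal that would show which case applies.

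**The case against.** The strongest reply is that 4.5.2 never says survival is the *only* thing to be collected, and that section 8 continues to apply.

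- **Adverse events.** A reader might infer that withdrawn children give no further adverse event data. The document does not support that. 8.1 and 8.2 exempt nobody, and 8.2 has the investigator ask about events at every contact, which would include an answered survival call. What remains is narrower: 4.5.2 does not refer to section 8, gives no timing for its calls, and so does not ensure that any contact covers the 30 days.
- **Stopping drug and leaving the study.** A reader might infer that these are always the same. They are not. Step 10 of 6.0 has a child with no improvement taper early, attend the coordinator visit and go on to crossover. Unscheduled visits for side effects include the NCCPC-R and Questionnaire #2. Those children are affected only if they are then withdrawn.
- **Missing pairs.** Not every withdrawn child lacks a gabapentin–placebo pair. Nor is an analysis of all randomized children impossible, since scores from before withdrawal exist.
- **Usefulness.** Forms completed after stopping cannot recreate a missing pair, and under the present 7.3 they would go unused. This objection stands, and it is why 7.3 has to change as well.
- **Consent wording.** It is tempting to set the 4.5.1 contact condition against 9.1, where "attempts should be made to obtain permission to collect at least vital status". But 9.1 concerns revoked authorization to use health information, a different act from leaving the study, so no contradiction is shown.

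**Conclusion.** The point holds for formally withdrawn children, and above all for those the site withdraws under 5.5 while consent still stands. For them the only follow-up named is a non-endpoint. Outcome forms, the reason for stopping and adverse event contact are not planned, and 4.5.2 is not aligned with 8.1 and 8.2. Sections 4.5.1 and 5.5 also disagree on whether withdrawal for missed doses is optional or mandatory.

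The consequence is a risk of bias more than a loss of power. Its size is not known, because the plan gives no withdrawal rate and the effect in withdrawn children is unobserved. The tabulated means, 13.5 to 7.5 points when d = 0, rest on assumed withdrawal of 10% to 50%; with d = 15 the bias is nil. The power figures rest on an assumed two-sided alpha of 0.05. The text should be changed, but the point does not invalidate the design.

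**What to change.** 1. **4.5.2.** Add to the survival contact, with the caregiver's permission: NCCPC-R and Questionnaire #2 at the time of withdrawal, and at the remaining scheduled time points where the family agrees; the main reason for stopping; and adverse events to 30 days after the last dose, with a reference to 8.1 and 8.2.
2. **4.3, 4.5.1 and 5.5.** Reconcile the optional and mandatory wording on withdrawal for missed doses; which rule applies is for the investigators to decide. Separate stopping study drug from leaving the study, so that the first does not end data collection.
3. **7.3.** Analyse data from all randomized children, including scores obtained before and at withdrawal, and state how scores obtained after stopping are used. Keep the compliant set as a sensitivity analysis.

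**Cost.** Wording, one further adverse event contact per withdrawn family, and the forms. By the plan's own estimate each form takes about 5 minutes, so both take 10 minutes at withdrawal. A family withdrawn just after Day 13 that agreed to all four remaining time points would spend a further 4 × 10 = 40 minutes. Some families will decline.
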